4.3 Secondary Objectives

Secondarily, this study aims to explore the effect of the intervention on patients' anxiety.

Finally, it seeks to explore the differences that may exist between an assessment of pain and anxiety made by patients (feelings of pain and anxiety) and that made by caregivers (estimated pain and anxiety) as well as the possible determinants of these differences, if they exist (patients: sex, age, origin, level of education / caregivers: sex, age).

4.4 Safety Objectives

Non-applicable.

5. STUDY OUTCOMES

5.1 Primary Outcomes

The primary outcome of this study will be patients' assessment of the intensity and unpleasantness (emotional component) of their pain during the insertion of the PIC.

5.2 Secondary Outcomes

The secondary outcomes of this study will be patients' assessment of their anxiety at PIC insertion and caregivers' assessment of patients' pain intensity and unpleasantness and anxiety at PIC insertion (Singer et al., 1999).

Other co-variables will be reported in the CRF to the extent that they may influence primary or secondary outcomes:

- The intensity and unpleasantness of pain and anxiety level assessed by patients prior to the CIP;
- Reason for consultation (internal medicine, traumatology or surgery);
- Any painkillers already given/ongoing in the ED (what, when, administered by whom);
- The caregivers' behaviour during the procedure;
- The patients' algic behaviour during the procedure;
- Procedure' characteristics (location, caliber, number of attempts, difficulties and complications encountered);
- Report of a possible fear of needles (« Are you generally afraid of needles? »);
- Report of a possible chronic pain (« Do you suffer from chronic pain, i.e. that has lasted for more than three months? ») and chronic painkillers consumption.

The sex, age, origin and educational background of patients, as well as the sex and age of caregivers, will also be reported to the extent that they may influence caregivers' assessment of patients' pain intensity and unpleasantness and anxiety level (Li et al., 2001; Nevin, 1996; Singer et al., 1999).

Finally, in the second phase, a unique coded number related to the study (study number) will be assigned to each caregiver and reported in the CRF when the PIC is inserted. If needed, it will allow the analysis of data by grouping patients by caregiver.

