4.2 Primary Objective

The primary objective of this study is to determine if the use of a positive information, avoiding negative words and suggesting specific notions of control and comfort related to the procedure, when inserting a PIC in the ED, reduces pain intensity when compared to the usual language practices.

The primary objective is also to determine if this effect is comparable, whether the message is delivered by a standardized audio recording or by the caregiver performing the procedure.

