The study is divided into two phases for organizational reasons. Indeed, it implies a perfect understanding and cooperation of the caregivers who perform the PIC insertion, their verbal and non-verbal behaviour should not interfere with the progress of the study. Thus, planning two successive arms, with an appropriate information session in each phase, instead of four arms conducted simultaneously at the same time, will limit unnecessary confusion and loss of included patients.

The variables will be reported in a standardized manner in the CRF in the following order:

- Before the insertion of the PIC:
 - Patient's identification number;
 - Inclusion and exclusion criteria;
 - Reason for consultation;
 - Antalgia already given/ongoing in the ER;
 - Patient's VAS relative to pain intensity, discomfort and anxiety.
- Around the insertion of the PIC:
 - Caregiver's behaviour.
- During the insertion of the PIC:
 - Message delivered;
 - Patient's behaviour.
- After the insertion of the PIC:
 - Procedure's characteristics (location of the PIC, PIC caliber, number of attempts before successful installing the PIC, difficulties and complications encountered);
 - Patient's VAS relative to pain intensity, discomfort and anxiety;
 - Report of a possible fear of needles (« Are you generally afraid of needles? »);
 - Report of a possible chronic pain (« Do you suffer from chronic pain, i.e. that has lasted for more than three months? ») and chronic painkillers consumption;

- Patient's demographics;
- Occurrence of potential inconveniences;
- Obtaining written consent;
- Caregiver's study number (only for the second phase);
- Caregiver's VAS relative to patient's pain intensity, discomfort and anxiety level;
- Caregiver's demographic characteristics.

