Caregivers' behaviour will be assessed according to the criteria described by Kaptchuck (Kaptchuck et al., 2008) during the procedure. The algic behaviour of patients during the PIC insertion will also be evaluated using the Algoplus scale (Rat et al., 2011). These two behavioural evaluations will be the subject of a one-day « Rating » pilot phase, during which co-investigators will be asked to rate some of the same patients when a PIC is placed in order to ensure that their ratings are well correlated.

The characteristics of the procedure (location, caliber, number of attempts, difficulties and complications encountered), the demographic characteristics of the patients (sex, age, origin, level of education) and the demographic characteristics of the caregivers (sex, age) will be reported in the CRF after the PIC insertion. Patients will also be asked two questions (« Are you generally afraid of needles? », « Do you suffer from chronic pain, i.e. that has lasted for more than 3 months? ») to contextualize their VAS and chronic analgesics use will be reported.

Finally, in the second phase, a unique identifier related to the study (study number) will be assigned to each caregiver and entered in the CRF when the PIC is placed. If necessary, it will allow the data analysis by clustering patients by caregiver to account for the natural clustering of patients by caregivers and allow for a multi-level analysis of the caregiving effect. This identifier consisting of numbers and letters will be created from elements of the caregiver's personal identifiers that are not recognizable for a person who has not been involved in the study (e.g. D_F9B0). The identifying elements themselves will not be collected. The coding key for this study number will only be known to co-investigators collecting the data and the person in charge of monitoring the protocol. Caregivers themselves will only be informed of their code (not of the coding key). The principal investigator will not participate in data collection. When entering data into the Excel database, this study number will be coded again. That way, caregivers will not be identifiable for those performing the analysis (PI).

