11.4.2 Primary Analysis

The primary analysis will compare the pain intensity and unpleasantness after the PIC insertion as measured by VAS. The VAS will be compared by Student t-test if the distribution is Gaussian or by Wilcoxon rank sum test if not. The analysis will be conducted according to the « intention to treat » principle, which will include all randomized patients.

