11.4.3 Secondary Analyses

The secondary analysis will compare the pain intensity and unpleasantness after the PIC insertion measured by VAS. The VAS will be compared by Student t-test if the distribution is Gaussian or by Wilcoxon rank sum test if not. The analysis will include only those patients for whom the message has been fully delivered.

The analysis of the secondary objectives, i.e. the intensity of anxiety, also measured by VAS, will focus on the comparison of VAS per Student t-test if the distribution is Gaussian or Wilcoxon rank sum

test if not. The same will be true for the caregivers' assessment by VAS of the patients' pain intensity and unpleasantness and anxiety level at PIC insertion.

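### The caregiver code is recorded only in phase 2 and its use is conditional, so repeated ratings by one caregiver in phase 1 cannot be linked; coding from the first patient is a cheap improvement

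*Combined protocol and SAP*

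**What the plan says.** Section 5.2 states that "in the second phase, a unique coded number related to the study (study number) will be assigned to each caregiver" and adds: "If needed, it will allow the analysis of data by grouping patients by caregiver". The CRF list in section 6.1 repeats the restriction: "Caregiver's study number (only for the second phase". The synopsis (Outcomes) agrees.

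Section 9.2.1 gives the purpose of the code, again conditionally and for phase 2 only: "to account for the natural clustering of patients by caregivers and allow for a multi-level analysis of the caregiving effect". The code is derived from personal identifiers, and of these it says: "The identifying elements themselves will not be collected". The phase 1 caregiver data are therefore behaviour, VAS ratings, sex and age, and none of these identifies a caregiver uniquely.

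Section 11 has no caregiver term. For patient pain, section 11.4.2 says: "The VAS will be compared by Student t-test if the distribution is Gaussian or by Wilcoxon rank sum test if not". Section 11.4.3 applies the same tests to caregiver ratings: "The same will be true for the caregivers' assessment by VAS of the patients' pain intensity and unpleasantness and anxiety level at PIC insertion".

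Sections 3.2 and 4.3 set the aim of exploring differences between patient and caregiver assessments and their possible determinants, including caregiver sex and age. Section 11 gives no analysis for those determinants.

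**The concern.** The protocol recognises that patients are clustered by caregiver, records the means of handling this in one of the two phases, and commits to using it in neither. No criterion says when the grouped analysis would be needed.

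The exposed analysis is the one on caregiver characteristics. Sex is constant within a caregiver and age nearly so. Several ratings from one caregiver therefore carry less information about these characteristics than the same number of ratings from different caregivers, and an analysis that counts each rating as independent gives standard errors that are too small. In phase 2 the code allows a correction. In phase 1 it does not exist and cannot be reconstructed afterwards.

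A second, smaller exposure is the message effect in phase 2. Section 8.1.1 encourages caregivers to formulate their own variant of the message, so its effect may differ between caregivers. The planned test makes no allowance for that.

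**Working it through.** **1. The plan's sample size.** Section 11.2 gives a difference of 13 mm, SD 24 mm, 80% power and alpha 5%. The two-sided normal formula is n = 2(1.96 + 0.8416)² × 24² / 13² = 53.5, so 54 per arm. The exact t-test gives 54.5, so 55, as stated. This figure assumes independent patients. With 60 randomised per arm and 10% lost, 60 × 0.9 = 54 per arm remain, or 108 per phase. That number is used below.

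**2. Caregiver-level determinants.** The documents give neither the number of caregivers (K) nor the intraclass correlation (ICC). I assume K = 20 to 40 and ICC = 0.1 to 0.2. With m = 108/K ratings per caregiver:

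- design effect DE = 1 + (m − 1) × ICC
- actual type I error of a nominal 5% test = 2[1 − Φ(1.96/√DE)]

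| K | m | ICC | DE | Effective n (108/DE) | Type I error, formula | Type I error, simulated |
|---|---|---|---|---|---|---|
| 40 | 2.7 | 0.1 | 1.17 | 92 | 7.0% | 8.0% |
| 40 | 2.7 | 0.2 | 1.34 | 81 | 9.0% | 11.4% |
| 20 | 5.4 | 0.1 | 1.44 | 75 | 10.2% | 10.9% |
| 20 | 5.4 | 0.2 | 1.88 | 57 | 15.3% | 17.3% |

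The simulation (8,000 runs per row) assigns patients to caregivers at random, makes half the caregivers of each sex, and compares ratings by caregiver sex with an ordinary t-test. It runs a little above the formula because caregivers then have unequal numbers of patients. Together the two give roughly 7% to 17%.

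**3. Message against control, caregivers differing only in level.** Section 6.2.1 randomises individual patients in blocks of 4 and 6, without stratification by caregiver. I simulated 108 patients under such blocks, with K = 20 or 40 and ICC 0.1 or 0.2. The t-test standard error averaged 99% to 100% of the true one, and type I error was 5.0% to 5.1%.

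**4. Message against control in phase 2, effect varying by caregiver.** Let τ be the between-caregiver SD of the message effect (assumed 4 to 8 mm, K = 10 to 30).

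- Base variance of the arm difference: 2 × 24²/54 = 21.3
- Extra variance: τ²/K
- τ = 8, K = 10: 64/10 = 6.4, and (21.3 + 6.4)/21.3 = 1.30. Since √1.30 = 1.14, the planned standard error is about 12% too small (1/1.14 = 0.88). Type I error is 8.6% by formula and 8.5% simulated with ICC 0.1.
- τ = 4, K = 30: 16/30 = 0.53, ratio 1.025. Type I error is 5.3% by formula and 5.6% simulated.

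**The case against.** There is a reasonable case for the plan as written.

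- **The phase 2 restriction has a rationale.** In phase 1 the message is a recording and the caregiver is blinded, so the caregiver is not the vector. Coding staff also has a confidentiality cost that sections 9.2.1 and 12.5 take seriously. This explains the choice, but caregivers still rate patients in phase 1 and the determinants aim is not limited to phase 2.
- **Phase 2 clustering is foreseen.** Section 9.2.1 names it and mentions a multi-level analysis. Independence is thus the default there, not a settled decision. That stands; what is missing is a stated model in place of a condition without a criterion.
- **The determinants analysis is exploratory.** Section 11 specifies no test of caregiver sex or age. The comparison of caregiver ratings that section 11.4.3 does specify follows the randomised arms, which individual randomisation largely protects. This stands and limits the weight of the point.

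Two stronger readings are tempting, and the documents support neither.

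- A reader might infer that leaving out the caregiver spoils the primary test, for instance by making its standard error too wide when caregivers differ in level. That would need arms balanced within caregiver, which section 6.2.1 does not provide. Under its blocks the standard error is right to within about 1%.
- A reader might infer that a phase 1 code would rescue the comparison of vectors. Section 4.2 does make recording against live delivery part of the primary objective: "The primary objective is also to determine if this effect is comparable, whether the message is delivered by a standardized audio recording or by the" (the sentence ends by naming the person who inserts the catheter). But the phases are sequential, the vector is not randomised, and section 11 gives no analysis for it. It is also imprecise before any clustering: with 55 per arm in four arms, the difference between the two message effects has a standard error of 24 × √(4/55) = 6.47 mm, hence a 95% half-width of 1.96 × 6.47 = 12.7 mm. A code in both phases would only permit adjustment for caregivers who appear in both.

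**Conclusion.** The point holds as a cheap improvement, with a deadline. Without a phase 1 code, an analysis of caregiver sex and age as determinants of the rating gap has to treat repeated phase 1 ratings as independent. The resulting type I error is roughly 7% to 17% instead of 5%, given 20 to 40 caregivers and an ICC of 0.1 to 0.2. Both ranges are assumptions; fewer ratings per caregiver or a lower ICC would shrink the problem.

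The randomised message comparison is not in doubt in phase 1. In phase 2 it is affected only if the message effect varies between caregivers. Over the assumed range, type I error runs from a little above 5% to about 8.5%, the upper figure needing strong variation (SD 8 mm) among only 10 caregivers. The vector comparison has larger difficulties of its own, which this change does not resolve.

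**What to change.** **Data collection.** Record the same coded caregiver number from the first phase 1 patient. Remove the phase 2 restriction in the synopsis and in sections 5.2, 6.1 and 9.2.1, and add the line to the phase 1 CRF. The second coding at database entry (section 9.2.1) should map each caregiver to the same value in both phases, or the link is lost.

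**Analysis.** In section 11, replace the conditional use with:

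- for caregiver-rated outcomes and for the determinants of the rating gap, in both phases, a linear mixed model with a random caregiver intercept;
- for the phase 2 patient VAS, a pre-specified sensitivity analysis that adds a random message-by-caregiver effect. The rule should be fixed in advance: if that variance is estimated at zero or the model does not converge, the random-intercept model is reported.

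**Cost.** One CRF line in phase 1, using a coding and confidentiality procedure already designed, plus protocol wording. Staff are coded earlier than now planned, and the analysis is slightly more complex. The data-collection change has to be made before phase 1 recruitment starts; the model can be added at any time before the data are analysed.

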5.3 Safety Outcomes

Non-applicable.

6. STUDY DESIGN

6.1 General study design and justification of design

It is an interventional, prospective, randomized, active-controlled, monocentric intervention study. It will take place in the LUH ED between October 2017 and October 2019. All patients admitted to this service will be eligible for inclusion. Data collection will be possible every day of the week between 7am and 10 pm in order to obtain a sample that is as representative as possible of an ED's population. In order to be able to cover as many hours as possible, the co-investigators will divide them among themselves and, at each intervention, only one of them will be present. Dr [name] and Dre [name] will not participate in data collection.

After consulting the patient's medical records in the ED and checking with the patient's caregivers that there are no exclusion criteria, the co-investigators will introduce themselves to the patients and invite them to participate in the study. The co-investigators will explain to the patients that, given the fact that their medical care involves the insertion of a PIC, they are eligible for this study aimed at improving the care of patients visiting the LUH ED during such an act. Should patients require additional information, the co-investigators will simply state that the study's primary objective is to assess the technical characteristics of the PIC insertion. At this stage, only a verbal agreement will be required. After verifying that all inclusion criteria have been met, that none of the exclusion criteria are applicable and obtaining a verbal consent, patients will be randomized in a 1:1 ratio between the two arms of the study, in a double-blind design (patient, caregiver, co-investigator) in the first phase and in a single-blind design (patient) in the second phase. The co-investigators will collect some additional data in a standardized manner by following the CRF and then report to the caregivers that they can prepare the patients for PIC insertion (installation of the tourniquet, vein tracking and site disinfection). In the first phase, a test audio clip and a recorded introductory audio clip will be played to the patients before the caregivers prepare them for the procedure. Once these preparations are completed, the co-investigators will play the recorded audio intervention or control message to the patients in the first phase or the caregivers will deliver one of the two alternative messages directly before puncturing the patients' vein in the second phase. In both cases, the co-investigators will complete the collection of data according to the CRF, first from patients and then from caregivers. Once all the data has been collected, a complete information sheet and consent form will be provided to the patients, along with additional explanations when requested. Patients will have a minimum of 15 minutes to sign the consent form. Excluding this 15 minutes reflection period, participation in the study should not exceed 20 minutes and will be unique.

The study is divided into two phases for organizational reasons. Indeed, it implies a perfect understanding and cooperation of the caregivers who perform the PIC insertion, their verbal and non-verbal behaviour should not interfere with the progress of the study. Thus, planning two successive arms, with an appropriate information session in each phase, instead of four arms conducted simultaneously at the same time, will limit unnecessary confusion and loss of included patients.

The variables will be reported in a standardized manner in the CRF in the following order:

- Before the insertion of the PIC:
 - Patient's identification number;
 - Inclusion and exclusion criteria;
 - Reason for consultation;
 - Antalgia already given/ongoing in the ER;
 - Patient's VAS relative to pain intensity, discomfort and anxiety.
- Around the insertion of the PIC:
 - Caregiver's behaviour.
- During the insertion of the PIC:
 - Message delivered;
 - Patient's behaviour.
- After the insertion of the PIC:
 - Procedure's characteristics (location of the PIC, PIC caliber, number of attempts before successful installing the PIC, difficulties and complications encountered);
 - Patient's VAS relative to pain intensity, discomfort and anxiety;
 - Report of a possible fear of needles (« Are you generally afraid of needles? »);
 - Report of a possible chronic pain (« Do you suffer from chronic pain, i.e. that has lasted for more than three months? ») and chronic painkillers consumption;

- Patient's demographics;
- Occurrence of potential inconveniences;
- Obtaining written consent;
- Caregiver's study number (only for the second phase);
- Caregiver's VAS relative to patient's pain intensity, discomfort and anxiety level;
- Caregiver's demographic characteristics.

6.2 Methods of minimising bias

6.2.1 Randomisation

In the first phase of the double-blind study, a randomization method by permutation of blocks of 4 and 6 patients will be used. The principal investigator, who will not collect data, will create the randomization list and hold the randomization seed.

In the second phase, only patients will be blind, but the assignment of one of the two messages will also be done by block permutation of 4 and 6.

In both phases of the study, randomization will occur immediately after verbal consent, before the intervention or control message is delivered.

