6.2.2 Blinding procedures

During the first phase, the allocation of the arm « control message » or of the arm « intervention message » will be determined by a code written on a card inside a sealed and opaque envelope, prepared by the principal investigator. This code will indicate the number, between 1 and 130, of the audio track to be played to the patient and will be recorded in the CRF. In the second phase, the note « control message » or « intervention message » written on the card will indicate to the caregivers the message to be delivered and will be reported in the CRF. Envelopes will be numbered consecutively, and the co-investigators will open them consecutively, noting each time the opening date. The principal investigator will regularly verify that the order of opening is respected by checking the number of envelopes opened and the opening dates against the number of patients included in the study.

The first phase of the study will be carried out in double blind (patient, caregiver, co-investigator) thanks to the coding of audio recordings. In the second phase, only patients will be blinded to the tested component.

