7.3 Assignment to study groups

After verifying that all inclusion criteria have been met, that none of the exclusion criteria are applicable and that each participant has given his or her verbal consent, each participant will be randomized in a 1:1 ratio between the two arms of the study using the opaque and sealed envelopes mentioned in section 6.2.2 « Blinding procedures ».

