9.2 Assessments of outcomes

9.2.1 Assessment of primary and secondary outcomes

The primary outcomes, the intensity and unpleasantness (emotional component) of pain experienced by patients during the PIC insertion, will be measured using a Visual Analog Scale (VAS) (Lang et al., 2014; Pagé et al., 2012). Patients' anxiety, as a secondary outcome, will also be measured by VAS. These three measurements will be performed by using three rulers after the PIC is inserted. These three rulers, with three different color codes to distinguish them, will be presented to the patients who will move the three sliders on a line going from one extreme to the other (No pain / Worst pain imaginable; Experience not at all unpleasant / Most unpleasant experience possible; Not at all anxious / Extremely anxious) and corresponding, on their other side, to a value between 0 and 100 mm on a 100 mm long line. This numerical value measured in millimetres will be reported in the CRF by the co-investigators. Patients will be asked to rate their overall feelings after the PIC insertion regarding these three aspects. The co-investigators will ensure that the caregivers do not become aware of the patients' responses.

As for caregivers' assessment of patients' pain intensity and unpleasantness and anxiety, these secondary outcomes will also be measured using the three VAS, this time in paper format and reported in the CRF after the PIC insertion. Caregivers will mark their estimation by tracing a line on each of the three VAS once they have completed their procedure, making sure that patients do not read their answers. The co-investigators will then measure the distance between the 0 extreme and the line traced by the caregivers in millimetres and report this numerical value in the CRF.

Before the PIC insertion, patients will assess the intensity and unpleasantness of any pre-existing pain and their basal anxiety level with these same three VAS. This will give a baseline value for these three measures. These values will be reported in the CRF before the PIC is inserted, along with the reason for consultation (internal medicine, traumatology or surgery) and any painkillers already given/ongoing in the ED.

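### In phase 2 the envelope naming the arm is opened before the baseline VAS is recorded, so the baseline is taken by someone who knows the allocation

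*Combined protocol and SAP*

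**What the plan says.** Five statements in the combined protocol and SAP bear on the order of events.

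- Section 6.2.1 fixes when randomisation happens: "In both phases of the study, randomization will occur immediately after verbal consent, before the intervention or control message is delivered".
- Section 7.3 says how it is done: participants are "randomized in a 1:1 ratio between the two arms of the study using the opaque and sealed envelopes".
- Section 6.2.2 says who opens the envelopes: "Envelopes will be numbered consecutively, and the co-investigators will open them consecutively, noting each time the opening date". It also says what the card shows. In phase 1 it is only a track number between 1 and 130. For phase 2: "In the second phase, the note « control message » or « intervention message » written on the card will indicate to the caregivers the message".
- Section 6.1, in the sentence directly after the one on randomisation, continues: "The co-investigators will collect some additional data in a standardized manner by following the CRF and then report to the caregivers". Only then does the caregiver begin preparing the patient.
- The CRF order in section 6.1 ends its pre-insertion block with "Patient's VAS relative to pain intensity, discomfort and anxiety". Section 9.2.1 confirms that this is the baseline: "Before the PIC insertion, patients will assess the intensity and unpleasantness of any pre-existing pain and their basal anxiety level with these same three VAS".

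Section 6.1 also says that a single co-investigator attends each intervention, and section 6.2.2 that in phase 2 only the patient is blinded.

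**The concern.** A baseline is useful because the allocation cannot have influenced it. In phase 2 the person who presents the rulers, explains them and writes down the readings already knows which message will follow. Any difference between arms in how the scores are elicited would look like a baseline imbalance, and would carry into any analysis that uses those scores. Section 5.2 lists the pre-insertion pain and anxiety scores first among the co-variables that may influence the outcomes, so such use is foreseeable.

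The problem also differs between phases. Section 4.2 makes comparability of the effect across audio and caregiver delivery part of the primary objective, and the Study Schedule describes the phases as identical apart from the vector. As written, one baseline is taken blind and the other is not. The protocol recognises this type of hazard: for phase 1, section 7.1 excludes cases in which the co-investigator knows the assigned message in advance.

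A second, smaller consequence applies to both phases. A patient who becomes unstable, loses capacity or withdraws between the envelope and the message has already been randomised. Section 7.4 then requires all data except sex and age to be destroyed, although section 11.4.2 promises an analysis of every randomised patient.

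**Working it through.** The point rests on the order of steps, not on a formula.

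**1. Order in the text (phase 2).** Putting sections 6.1, 6.2.1, 6.2.2 and 7.3 together gives:

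1. eligibility verified and verbal consent obtained;
2. envelope opened by the co-investigator, arm shown in words;
3. pre-insertion CRF items, ending with the three baseline VAS;
4. caregiver prepares the patient;
5. message, then puncture.

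The baseline VAS cannot come before step 2 on this text. It is study data and needs verbal consent, and randomisation follows that consent immediately. With one co-investigator present, the person at step 2 is the person at step 3.

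**2. Check against the Study Schedule.** The phase 2 screening column lists criteria (-2), verbal consent (-4), randomisation (-1) and CRF measurement (-2), in that row order.

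- Read as durations: 2 + 4 + 1 + 2 = 9 of the 10 minutes before the intervention, and the debriefing entries give 2 + 8 = 10 minutes. The row order agrees with the text.
- Read as clock times: measurement at -2 would precede randomisation at -1. Consent at -4 would then precede the eligibility check at -2, and randomisation would no longer follow consent immediately. This contradicts sections 6.1 and 6.2.1.

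The duration reading is the consistent one.

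**3. Search for a safeguard.** Nothing says that the phase 2 envelope stays sealed until the baseline is recorded, or that only the caregiver reads the card. Section 6.2.2 has the co-investigators open it.

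**4. Effect on the planned analyses.** Sections 11.4.2 and 11.4.3 compare post-insertion VAS by t-test or Wilcoxon rank sum test, with no baseline term. In an adjusted model, the bias from a spurious baseline shift between arms is slope × shift. The planned tests have no slope, so the bias by this route is 0 mm. The documents give neither a slope nor a shift for any other analysis, so no size can be computed there.

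**5. Post-randomisation losses.** Section 11.2 allows 10% for missing values and refusals after randomisation: 0.10 × 60 = 6 patients per arm. The documents do not split these by time of loss, so the share falling between envelope and message is unknown.

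**6. Sample size.** With a 13 mm difference, SD 24 mm, two-sided alpha 0.05 (sidedness assumed) and 80% power, the normal formula gives 54 per arm and the t-distribution 54.5, rounded up to 55. This reproduces the stated 55. It makes no use of baseline, so reordering does not alter it.

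**The case against.** The strongest reply is that little depends on this baseline. The primary and secondary tests ignore it. The patient, who is blinded, moves the slider, and the co-investigator only reads a millimetre value from the back of the ruler (section 9.2.1). Patients are not told that communication is being studied or that there are two messages (section 6.2.3). Phase 2 is openly single-blind, and the same unblinded co-investigator later collects the post-insertion VAS, an exposure that reordering leaves untouched. All of this stands, and it limits the weight of the point.

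It is also fair that no single sentence puts the envelope before the baseline VAS; the order has to be assembled. But the pieces fit only one way, and if the sponsor intended the baseline first, the text still needs correcting.

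The loss argument is modest. The schedule gives 2 minutes to pre-insertion CRF work, to which preparation time is added, and eligibility is re-checked at the bedside beforehand (section 7.2). Refusal of written consent comes at debriefing (section 2.7), and no change in envelope timing can move it.

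A reader might infer that the phase 2 treatment effect itself is biased, and put a figure on it. For example, a 5 mm baseline shift with a slope of 0.3 to 0.6 gives 1.5 to 3.0 mm, or 12% to 23% of 13 mm. The documents do not support this. Both inputs are assumptions with no source in them, and the adjusted model to which they would apply is not planned.

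**Conclusion.** The point holds for phase 2. As written, the three baseline VAS are elicited after the arm has been disclosed to the only co-investigator present. The conclusion assumes that opening the envelope is the act of randomisation, as section 7.3 indicates, and that the schedule entries are durations.

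The planned unadjusted comparisons are not biased by this route. What is exposed is the credibility of the phase 2 baseline table and of any adjusted or change-from-baseline analysis, by an amount that the documents do not allow one to estimate. Phase 1 has no blinding problem here because its card carries only a track number. The avoidable post-randomisation losses are real in principle, in both phases, but their number is unknown and probably small given the short interval. The amendment is worth making because it is simple; the point does not threaten the primary result.

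**What to change.** Amend sections 6.1 and 6.2.1 and the Study Schedule so that, after verbal consent, the co-investigator first records the pre-insertion CRF items and the three baseline VAS, and only then opens the next envelope. Open it as late as is practical before the message. In phase 2, leave the caregiver enough time to read the card and the key-element reminder described in section 8.1.1. Opening after baseline but before the patient is prepared already meets the blinding concern; opening later also reduces post-randomisation losses. State in the schedule whether its minute entries are durations or clock times.

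Blinding requires the change in phase 2 only. Using the same order in phase 1 is optional; it would keep the phases identical and move some exclusions to before randomisation. Refusals at debriefing would remain post-randomisation losses.

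The cost is a small change in bedside workflow, mainly the timing of the handover of the card to the caregiver in phase 2. It needs no new data, staff or change in sample size.
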